## 9 General Specifications for Data Analyses

All analyses will be prepared by planned dose level, unless indicated otherwise.

Details on PK data presentation can be found in [Section 16.1](#).

CCI

**Data handling after cut-off date:**

In general, this is not applicable, as the analyses described will be conducted after all subjects have completed their involvement in the study.

**Pooling of centers:**

Because of the small number of subjects in each center, data will be pooled across centers.

**Significance level:**

There is no formal significance level for this study and all analyses are considered descriptive.

**Presentation of continuous and qualitative variables for Demographics and Other Baseline Characteristics, Efficacy, and Safety:**

Continuous variables will be summarized using descriptive statistics, i.e.

- number of subjects (N), number of nonmissing values (n)
- mean, standard deviation
- median, 25th Percentile - 75th Percentile (Q1-Q3), minimum, and maximum

If there are no missing values this should be indicated by a 0.

Qualitative variables will be summarized by counts and percentages.

Unless otherwise stated, the calculation of proportions will be based on the number of subjects of the analysis set of interest. Therefore, counts of missing observations will be included in the denominator and presented as a separate category.

In case the analysis refers only to certain visits, percentages will be based on the number of subjects still present in the study at that visit, unless otherwise specified.

**Definition of baseline:**

In general, the last nonmissing measurement prior to the first study treatment will serve as the baseline measurement. If an assessment is planned to be performed prior to the first dose of study treatment in the protocol and the assessment is performed on the same day as the first dose of study treatment, it will be assumed that it was performed prior to study treatment administration if assessment time point is not collected or is missing. If assessment time points are collected, the observed time point will be used to determine predose on Study Day 1 for baseline calculation. Unscheduled assessments will be used in the determination of baseline. However, if time is missing, an unscheduled assessment on Study Day 1 will be considered to have been obtained after study treatment administration.

**Definition of duration:**

Duration will be calculated by the difference of start and stop date + 1, if not otherwise specified (e.g., survival time (days) = date of death – date of first study treatment + 1).

The time since an event (e.g., time since first diagnosis) will be calculated as reference date minus date of event.

**Definition of study day/treatment day:**

Treatment day is defined relative to the date of first dose of any study treatment. Day 1 represents the first day of treatment; the day before is defined as Day –1 (no Day 0 is defined).

**Definition of treatment period:**

On-treatment period is defined as the time from the first dose of study treatment through minimum (30 days + last dose of study treatment, start day of new anticancer drug therapy – 1 day).

**Conversion factors and reporting standards:**

The following conversion factors will be used to convert days into months or years:

1 week = 7 days, 1 month = 30.4375 days, 1 year = 365.25 days.

For reporting conventions, mean, median, Q1, Q3, min, and max will have the same precision (number of digits) as SDTM data for non-derived values; standard deviation will have one additional decimal place. Percentages will be reported to one decimal place. The rounding will be performed to closest integer/first decimal using the common midpoint between the two consecutive values (e.g., 5.1 to 5.4 will be rounded to an integer of 5, and 5.5 to 5.9 will be rounded to an integer of 6).

**Unscheduled visits:**

Data collected at unscheduled visits will be included and analyzed in the same fashion as the data collected at scheduled visits except where otherwise noted in the sections that follow. Descriptive statistics (mean, StDev, median, minimum, maximum, and quartiles) by nominal visit or time point for safety endpoints such as laboratory measurements, ECGs, and vital signs will include only data from scheduled visits.

**Summary statistics over time:**

For descriptive statistics over time by nominal visit or time point (for non-PK data only), only those planned visits/time points that have at least 5 subjects overall (regardless of the number in each planned dosing cohort) will be included in the summary tables and figures. The exception is the End-of-Treatment and Safety Follow-up visits, which will be included in the summary statistics regardless of the number of subjects who completed the visit.

**Visit windowing:**

The assignment of visit window is described in [Table 2](#) for the purpose of by-visit analyses of laboratory assessment, vital sign, and ECG data:

- Baseline will be derived as described above.
- Both scheduled and unscheduled assessments are included for visit windowing.
- No visit windowing will be performed at End-of-Treatment or Safety Follow-up visits. Instead, the earliest nonmissing observation among the unscheduled or scheduled assessments for each visit will be used for the analysis.
- If there are multiple assessments for any specified visit and some of them are from scheduled visits with nonmissing assessment results, the assessment from scheduled visit that is closest to the planned study day will be used for analysis. If two scheduled visits are equally spaced around the assigned study day, the earlier of the two will be used.

- If there are multiple assessments for any specified visit and none of them are from scheduled visits, the assessment with nonmissing results and closest to the planned study day will be used for analysis.
- If there are two or more unscheduled assessments with nonmissing results and the same distance to the planned study day, the assessment prior to the planned study day will be used in deriving visit window. For example, if the lab assessment was done on both Study Day -1 and 1, then the assessment on Study Day -1 will be used for visit windowing.

**Table 2** Visit Window Definition for Safety Assessment

Assigned Study Day (Inclusive)		Planned Study Day (AWTARGET)	Analysis Visit (N) (AVISITN)	Analysis Visit (AVISIT)	Assessments
From (AWLO)	To (AWHI)				
-28	1		0	Screening	Lab, VS, ECG
-1	2	1	1.1	Cycle 1 Day 1	Lab, VS, ECG
7	9	8	1.8	Cycle 1 Day 8	Lab, VS, ECG
14	16	15	1.15	Cycle 1 Day 15	Lab, VS, ECG
21	23	22	1.22	Cycle 1 Day 22	Lab, VS
28	30	29	2.1	Cycle 2 Day 1	Lab, VS, ECG
42	44	43	2.15	Cycle 2 Day 15	Lab, VS
54	60	57	3.1	Cycle 3 Day 1	Lab, VS
68	74	71	3.15	Cycle 3 Day 15	Lab, VS
82	88	85	4.1	Cycle 4 Day 1	Lab, VS, ECG
96	102	99	4.15	Cycle 4 Day 15	Lab, VS
110	116	113	5.1	Cycle 5 Day 1	Lab, VS
124	130	127	5.15	Cycle 5 Day 15	Lab, VS

Further windows can be calculated based on the following general algorithm starting from the planned study day in Cycle X:

$$\text{Planned study days in Cycle X} = (X - 1) * 28 + 1 \text{ and } (X - 1) * 28 + 15$$

$$\text{Assigned study days (inclusive)} = [(X - 1) * 28 - 3] \text{ days to } [(X - 1) * 28 + 3] \text{ days}$$

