Tumor evaluation, staging u,v	X			X		X		X		Q 12 weeks		

Treatment cycles: 28 days; after treatment Cycle 7 (on Day 1 only) subjects will be assessed at the start of every third cycle (7+n×3).

aPTT = activated partial thromboplastin time; CD = cluster of differentiation; CT = computed tomography; ECG = electrocardiogram; DLT = dose-limiting toxicities; ECOG PS = Eastern Cooperative Oncology Group Performance Status;  $\beta$ HCG =  $\beta$ -human chorionic gonadotropin; HBcAb = hepatitis B core antibody; HBsAb = antibody to hepatitis B surface antigen; HBsAg = hepatitis B surface antigen; HCVAb = hepatitis C virus antibody; CCI [REDACTED]; Ig = immunoglobulin; IL = interleukin; INF = interferon; CCI [REDACTED]; MRI = magnetic resonance imaging; NK = natural killer; PBMC = peripheral blood mononuclear cell; PD = pharmacodynamic; CCI [REDACTED]; PK = pharmacokinetic; TNF = tumor necrosis factor; CCI [REDACTED]; TSH = thyroid-stimulating hormone; QTc = corrected QT interval.

- a Time window of assessment visits: Cycle 1 and 2:  $\pm$  1 day; every cycle thereafter:  $\pm$  3 days.
- b Screening tests must be performed within 21 + 7 days before the first administration of M4112, unless indicated otherwise.
- c All subjects should undergo an End of Treatment Visit after M4112 is discontinued for any reason. This visit should be performed within 7 days after the decision to discontinue study treatment but before any new antineoplastic therapy is started (if possible), whichever occurs earlier.
- d All subjects who discontinue M4112 treatment must undergo the End of Treatment Visit (within 7 days) and Safety Follow-up Visit (within 30  $\pm$  3 days) for full safety evaluation.
- e Inclusion/exclusion criteria should be reviewed before Cycle 1 Day 1 before the subject's enrollment, which needs to be confirmed by the Sponsor (see Section 5.3).
- f The physical examination at Screening will include, general appearance, skin, pulmonary, cardiovascular, gastrointestinal, external genitourinary only as medically relevant, lymphatic, neurologic and musculoskeletal systems, head/neck, extremities, eyes, ears, nose, throat, and cognitive status.

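### The SAP's formula for visit windows beyond Table 2 (Cycle 6 onward) is centred one day before planned Day 1 and provides no Day 15 window; the effect is confined to late-cycle by-visit summaries

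*SAP*

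**What the plan says.** SAP Section 9, under visit windowing, assigns laboratory, vital-sign and ECG records to analysis visits for the by-visit analyses. Table 2, "Visit Window Definition for Safety Assessment", gives a lower day, an upper day and a planned day for each visit through Cycle 5 Day 15. Examples are "54 60 57 3.1 Cycle 3 Day 1", "68 74 71 3.15 Cycle 3 Day 15" and "110 116 113 5.1 Cycle 5 Day 1". For anything later: "Further windows can be calculated based on the following general algorithm starting from the planned study day in Cycle X". Two expressions follow. The first gives two planned days per cycle, (X−1)×28+1 and (X−1)×28+15. The second gives a single range of assigned days, (X−1)×28−3 to (X−1)×28+3.

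The protocol sets the visit tolerance in Table 1, footnote a. The note headed "Time window of assessment visits: Cycle 1 and 2" allows ± 1 day in those two cycles and ± 3 days in every later cycle. Protocol Table 1 schedules Day 15 visits through Cycle 6 and Day 1 only from Cycle 7. Footnote k places core chemistry on Day 15 of Cycles 2 to 6. Footnote g places vital signs on Day 1 and Day 15 of every cycle. Footnote h places the later safety ECGs on Day 1 of Cycles 4 and 6 and of every second cycle after that.

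**The concern.** The window expression should be the planned day plus or minus the tolerance, and its lead-in says it starts from the planned day. It has instead dropped the +1 that turns (X−1)×28 into Day 1, and it has no counterpart for Day 15 even though the line above defines a planned Day 15. This is a stated rule that a programmer would code. Followed as printed, it excludes some visits that the protocol permits and leaves one scheduled laboratory and vital-sign visit with no analysis visit. The alternative is for the programmer to depart from the approved plan without a record. By-visit laboratory changes from baseline (SAP Section 15.4) help describe one of the primary safety endpoints, so the rule should be right even if few records depend on it.

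**Working it through.** **Inputs**
- Planned days: (X−1)×28+1 and (X−1)×28+15 (SAP Section 9).
- Printed window: (X−1)×28−3 to (X−1)×28+3 (SAP Section 9).
- Listed windows for Cycles 3 to 5 (SAP Table 2).
- Tolerance from Cycle 3: ± 3 days (protocol Table 1, footnote a).

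**Step 1: try to reproduce Table 2.** Cycles 3 to 5 are the listed cycles in which the ± 3-day tolerance applies. For X = 3, (X−1)×28 = 56. The printed window is therefore 53–59, while planned Day 1 is 57 and 57 ± 3 gives 54–60.

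| Visit | Planned day | Printed formula | Planned day ± 3 | Table 2 |
|---|---|---|---|---|
| Cycle 3 Day 1 | 57 | 53–59 | 54–60 | 54–60 |
| Cycle 3 Day 15 | 71 | none | 68–74 | 68–74 |
| Cycle 4 Day 1 | 85 | 81–87 | 82–88 | 82–88 |
| Cycle 4 Day 15 | 99 | none | 96–102 | 96–102 |
| Cycle 5 Day 1 | 113 | 109–115 | 110–116 | 110–116 |
| Cycle 5 Day 15 | 127 | none | 124–130 | 124–130 |

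The planned-day expression matches every target in the table. The printed window matches none of the six listed windows; planned day ± 3 matches all six. Relative to planned Day 1, the printed window runs from −4 to +2. Relative to planned Day 15 it ends 12 days too early: (X−1)×28+15 minus (X−1)×28+3 is 12.

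**Step 2: apply it where it is needed, from Cycle 6.**

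| Visit | Planned day | Printed formula | Planned day ± 3 | Permitted day lost | Extra day admitted |
|---|---|---|---|---|---|
| Cycle 6 Day 1 | 141 | 137–143 | 138–144 | 144 | 137 |
| Cycle 6 Day 15 | 155 | none | 152–158 | all | – |
| Cycle 7 Day 1 | 169 | 165–171 | 166–172 | 172 | 165 |
| Cycle 8 Day 1 | 197 | 193–199 | 194–200 | 200 | 193 |

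**Step 3: check whether records change visit.** The last Table 2 window ends on Day 130 and the printed Cycle 6 Day 1 window starts on Day 137, so they do not overlap. Later printed windows are 28 days apart and 7 days wide, so they do not overlap either. A record can be lost or wrongly admitted at a window edge, but it does not move to a different visit.

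**Step 4: see which outputs use the windows.** Section 15.4 takes the worst laboratory grade from any visit, scheduled or unscheduled, and shifts to the worst post-baseline grade. Section 15.5 uses the maximum on-treatment change in vital signs. Section 15.6 counts ECG abnormalities over the whole on-treatment period. The QTc plots in Section 15.6.1 stop at Cycle 2 Day 1. Baseline has its own definition in Section 9. What remains is descriptive statistics by visit, which Section 9 restricts to visits with at least 5 subjects overall, apart from the End-of-Treatment and Safety Follow-up visits (not windowed by study day).

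**The case against.** The best defence is that this is a slip with an obvious reading. The lead-in, both planned days and all six Cycle 3–5 rows point to planned day ± 3, and Table 2 itself governs every visit through Cycle 5, so the mismatches in those cycles touch no data. The Day 15 gap is essentially one visit, Cycle 6 Day 15, because the schedule shows Day 1 only from Cycle 7; later Day 15 vital signs enter only if footnote g is followed. Even the affected summaries may never be produced. About 24 monotherapy subjects were planned, the study was terminated early, and summaries need at least 5 subjects at the visit. Section 9 also says, under unscheduled visits, that descriptive statistics by nominal visit use scheduled data only, which might be taken to make the windows less important.

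All of this limits the size of the problem, and I accept it. It does not make the rule right: the windowing text says it serves the by-visit analyses, and it names no fallback to the nominal visit label.

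A reader might infer more than the documents support. One inference is that late records are assigned to the wrong visit; Step 3 shows they are not. Another is that late ECG visits fall in the Day 15 gap; they are scheduled on Day 1 only, so they meet only the one-day shift. A third concerns Table 2, where the Screening row (−28 to 1) and the Cycle 1 Day 1 row (−1 to 2) share Days −1 and 1. That might suggest that baseline is compromised, but baseline is derived separately as the last nonmissing pre-treatment value, so changes from baseline do not depend on those rows.

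**Conclusion.** The point holds as a small error in a stated rule. From Cycle 6, each Day 1 window is one day early: it excludes planned+3 and admits planned−4. The Cycle 6 Day 15 laboratory and vital-sign visit has no window. Later Day 15 vital signs are in the same position if footnote g is followed rather than the schedule columns. The consequence is limited to late-cycle by-visit descriptive summaries, mainly laboratory, and arises only if at least 5 subjects reach those visits. The documents do not say how many reached Cycle 6, so the number of records affected cannot be stated and may be nil.

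The safety conclusions drawn from worst grades, maximum changes and on-treatment incidence do not depend on this formula. Although treatment-emergent laboratory and vital-sign changes are a primary endpoint, the documents do not support reading this as a defect in the primary safety analysis as a whole. The conclusion assumes that the formula would be applied as printed.

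**What to change.** Replace the single window expression in SAP Section 9 with planned study day ± 3 for both visits:
- Day 1: (X−1)×28−2 to (X−1)×28+4. Cycle 6 gives 138–144.
- Day 15: (X−1)×28+12 to (X−1)×28+18. Cycle 6 gives 152–158.

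As a minor tidy-up, remove the overlap between the Screening and Cycle 1 Day 1 rows of Table 2, for example by ending Screening on Day −2, the day before the Cycle 1 Day 1 window opens. This leaves baseline unchanged.

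The cost is one corrected line, one added line and one table cell, made before database lock. No data collection or analysis method changes.

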#### Handling of missing data:

Unless otherwise specified, missing data will not be replaced.

In all subject data listings, imputed values will be presented and flagged as such.

Missing statistics (e.g., when they cannot be calculated) should be presented as “nd”. For example, if n=1, the measure of variability (StDev) cannot be computed and should be presented as “nd”.

Where tables are presented over different time points, the total of missing and nonmissing observations at each time-point should reflect the population still in the study at that time. This does not apply when imputations are made beyond study withdrawal. For example, if a subject is still in the study at the time-point but with missing data, they should be counted in the number of missing observations.

Handling of missing data for PK parameter calculations are discussed under [Section 16.1](#).

Pharmacokinetic parameters will be derived using the validated computer program Phoenix® WinNonlin® 6.4 or higher, and/or SAS® (Statistical Analysis System, [PPD](#)

Windows Version 9.4 or higher. All other analyses will be performed using SAS® Windows Version 9.4 or higher. For the outputs of the Bayesian two parameter logistic model updates, East 6.0 or R (version 3.1.0 or higher [3]) and the R package bcrm [4] or CRMpack or SAS proc MCMC will be used.

## 10 Study Subjects

The subsections in this section include specifications for reporting subject disposition and treatment/study discontinuations. Additionally, procedures for reporting protocol deviations are provided.

### 10.1 Disposition of Subjects and Discontinuations

The following will be summarized overall and by planned dose level, with the percentages calculated based on the number of subjects in the Screening Analysis Set.

- Total number of subjects screened (i.e., subjects who gave informed consent)
- Number of subjects who discontinued from the study prior to treatment overall and grouped by the main reason (e.g., the failed specific inclusion or exclusion criteria, withdrawal of consent)
- Number of treated subjects
- Number of subjects who completed the dose escalation period
- Number of subjects who discontinued the treatment, grouped by main reason
- Number of treated subjects who discontinued the study, grouped by main reason

The percentages for subjects treated will be based on the number of subjects in the safety population for each treatment sequence and on the number of screened subjects in the overall group.

In the corresponding individual listing, date of informed consent, protocol version, first and last

date of dosing and study termination date will be presented, as well as primary reason for study and treatment discontinuation.

The listing of screening failures will include the following information:

- Date of informed consent
- Protocol version
- Date of screening failure
- Reason for noninclusion

The disposition listings will be sorted by dose group and subject ID.

## 10.2 Protocol Deviations

### 10.2.1 Important Protocol Deviations

The following summary tables and listings of important protocol deviations will be provided (separately for pre-/postinclusion deviations):

- Frequency table per reason of important protocol deviations
- Listing of important protocol deviations

Important protocol deviations will be determined for all subjects by either medical or PK review processes or programming based on the inclusion/exclusion criteria or other criteria presented in the protocol or described in Section 18.1.

### 10.2.2 Reasons Leading to the Exclusion from an Analysis Set

The exclusion of subjects from analysis populations, e.g. due to clinically important protocol deviations, will be summarized by counts and frequencies for all occurring reasons of exclusion for each analysis population.

Exclusions will also be listed, including:

- Population that the subject is excluded from
- Reason of exclusion

## 11 Demographics and Other Baseline Characteristics

If not stated otherwise, summaries will be presented for the Safety Analysis Set.

## 11.1 Demographics

Demographic characteristics will be listed (sorted by dose group and subject ID) and summarized by dose group and overall as follows:

- Demographic characteristics
  - Gender: Male, Female
  - Race: White, Black or African American, Asian, American Indian or Alaska Native, Native Hawaiian or Other Pacific Islander, Not Collected, Other
  - Ethnic origin: Hispanic/Latino (Yes/No), Japanese (Yes/No)
  - Age (years): summary statistics
  - Age categories:
    - < 65 years, ≥ 65 years
    - < 65, 65 – 74, 75 – 84, ≥ 85
  - Eastern Cooperative Oncology Group (ECOG) Performance Status
- Physical measurements
  - Height (cm)
  - Weight (kg)
  - Body Mass Index (BMI) (kg/m^2)

Specifications for computation:

- Age [years] = (date of given informed consent - date of birth + 1) / 365.25
  - In case of missing day for at least one date, but month and year available for both dates:
    - For the derivation of age, the day of informed consent and the day of birth will be set to 1 and the formula above will be used
  - In case of missing month for at least one date, but year available for both dates:
    - For the derivation of age, the day and the month of informed consent and the day and month of birth will be set to 1 and the formula above will be used
- Site codes will be used for the determination of the subject's geographic region.

## 11.2 Medical History

Medical history will be coded using the most current available version of Medical Dictionary for Regulatory Activities (MedDRA). Medical history will be summarized as the numbers and percentages of subjects by MedDRA preferred term (PT) as event category and MedDRA primary system organ class (SOC) as summary category. Each subject will be counted only once within each PT or SOC.

Medical history will be displayed in terms of frequency tables: ordered by primary SOC and PT in alphabetical order.

A supportive listing of medical history data by subject will include all the relevant data fields as collected on the "Medical History" CRF pages.

### 11.3 Disease History and Prior Anti-Cancer Therapies

Information regarding disease characteristics collected on the "Disease History" CRF page will be summarized and/or listed as follows:

- Primary tumor histology
- Site and subsite(s) of primary tumor
- Time since initial cancer diagnosis (months), defined as (date of first study treatment – date of initial diagnosis)/30.4375
- Time since documented locally advanced, inoperable, or metastatic disease diagnosis (months), defined as (date of first study treatment – date of documented locally advanced, inoperable, or metastatic disease diagnosis)/30.4375
- Time since of last progression of disease prior to study entry (months), defined as (date of first study treatment – date of last disease progression)/30.4375
- TNM classification at initial diagnosis and at study entry

The prior anticancer treatments and procedures are collected under "Prior anti-cancer therapy", "Prior anti-cancer radiotherapy", and "Prior anti-cancer surgeries" pages from the CRF.

Prior anti-cancer drug therapy will be listed including the following information:

- Regimen number
- Intent and type of therapy
- Reason for discontinuation
- Best response
- Date of documented progression disease (if applicable)
- For each drug given as part of the regimen:
  - Name of drug (coding as described in Section 12)
  - Start and end date

Prior anti-cancer radiotherapy will be listed including the information:

- Regimen number
- Location
- Start and end dates
- Total dose

- Number of fractions

Prior anti-cancer surgeries will be listed including the following information:

- Name of surgery
- Date of surgery
- Intent of surgery
- Outcome of surgery

A summary of prior anti-cancer therapies will be added to the disease history, displaying number of surgeries, radiotherapy regimes and anti-cancer drug regimes.

Baseline characteristics with respect to vital signs, physical examinations, ECGs, and laboratory tests will be part of [Section 15 \(Safety Evaluation\)](#).

